9.2 Sample Size and Randomization

Sample Size Calculation/Power Analysis:

Primary Objective The power for the primary aim of this study was determined for change in the days percent abstinent from opioids on the Timeline Followback Interview (TLFB) between the study's two arms (MABT +TAU, and TAU only) from baseline to 6 months (R33 aim) and baseline to 12 months (R01 aim). The power analysis was based on the prior MABT SUD R01 study (N=187), in which the proportion of abstinent days for MABT + TAU was 88.6 compared to 80.0 for TAU at 12 month follow-up.[90] Unlike the count data used to assess the number of days abstinent, proportional data is based on exact binomial confidence intervals and thus provides reliable and appropriate data to use for sample size calculation. The magnitude of effect in this prior R01 is expected to be similar for baseline to 6 month (R33) and baseline to 12-month effect for MABT + TAU vs. TAU (R01) in the current study.

A sample of 330, with an expected loss to follow-up of 20%, allows for .80 power to detect a minimum difference in proportion in days abstinent between MABT and TAU of .14, alpha =.05, two-tailed. Loss to follow-up is not expected to vary significantly due to treatment assignment. Since the actual analyses allow GEE models to analyze five time points (0, 3, 6, 9, 12 months) simultaneously for the R01 study, power will very likely be higher than these conservative estimates.

Secondary Outcomes For comparison of treatment arms on measures of secondary outcomes, we will have 80% power to detect a minimum difference of 0.4 SD. For comparison of medication-assisted treatment retention rates, we hypothesize that retention rates at 12 months will be 60% in the TAU arm and 77% in the MABT arm. The comparison of proportions will have power of 80% to detect this difference. Exploratory Aim: at 6 months after 20% attrition, we expect the total sample to be N = 264 (132 per group) and assume the ability to detect, at minimum, a 15% difference between MABT and TAU groups in proportion of abstinent days. Under these assumptions, the power at 12 months to detect a group difference comparing those using substances at 6 months (nonresponders) in control to those using substances (nonresponders) at 6 months in MABT groups (who have been offered additional sessions) is .65 for a 40% non-responder rate (n = 53 per group). While underpowered, this exploratory aim would provide a reasonable sample size to estimate power for future related research questions and allows us to look at the question of MABT dose and re-engagement for those needing additional treatment support within the primary analysis.

Missing Data: We will evaluate differences in baseline characteristics between participants lost to follow-up versus those who are not. Missing data patterns will also be evaluated including the frequency and percentage of those missing for each variable and the distribution of the number of variables missing. In addition, data collected to the point of lost to follow-up will be compared to the data of those who complete the study to examine possible missing data mechanisms, e.g., missing completely at random (MCAR), missing at random (MAR), or not missing at random (NMAR). Sensitivity analyses will be performed to assess the possible impact of the missing data on the study results. We will consider various methods for missing TLFB including multiple imputation and pattern mixture models.[105] Similar methods will be used for other drug use and opioid craving. We anticipate there should be no missing data for retention since patients who are lost to follow-up are discharged from the program, therefore “missingness” is part of the variable definition.

Randomization: Randomization will be provided by the project statistician. Stratified randomization, by study site, baseline self-reported chronic pain, and gender, will be used to distribute participants evenly between the two treatment conditions at each facility and within each gender. Randomization will use a modified minimization method algorithm[96] based on an overall imbalance score which measures how far out of balance (within strata) the study is for a given set of random assignments to ensure approximately equal accrual into the two experimental arms and to facilitate concealment of treatment assignments.

Treatment Assignment Procedures

Research coordinators will use the randomization program developed by the project statistician to determine the treatment assignment group following baseline data collection. Participants will be informed of their assignment within one week of the initial appointment by the Research Coordinator. Prior MABT studies showed no loss due to randomization to treatment group, thus we do not expect randomization to precipitate significant attrition. The Research Coordinator at each facility will not be blind to condition and will inform participants of their treatment condition and MABT therapist.

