1.2 Secondary Objectives

1) To examine the effectiveness of MABT + TAU to improve mental and physical health compared to TAU only.

Hypothesis: MABT+TAU will result in significantly improved symptoms of mental health distress (depression, anxiety, trauma), emotion regulation, interoceptive awareness and mindfulness skills, and physical health distress and pain (symptoms, pain severity, pain interference) compared to TAU only from baseline to 12 months.

2) To examine the effectiveness of MABT + TAU to positively affect substance use related outcomes of craving and treatment retention compared to TAU only.

Hypothesis: MABT + TAU will result in significantly reduced craving for opioids, and significantly longer retention (days receiving medications), compared to TAU only from baseline to 12 months.

3) To explore the effectiveness of additional MABT dose offered at 6 months to those with continued substance use (nonresponders) compared to those with continued substance use at 6 months in TAU.

Hypothesis: Among participants in both groups who are using substances at 6 months, those in MABT group who receive additional MABT sessions (between 6-9 months) will

show improved substance use at 12 months compared to those in TAU.

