Secondary Objective 3 Hypothesis: Among participants in both groups who are using substances at 6 months, those in MABT group who receive additional MABT sessions (between 6-9 months) will show improved substance use at 12 months compared to those in TAU.

Exploration of the effectiveness of additional MABT dose offered at 6 months to those with continued substance use compared to those with continued substance use at 6 months in the TAU will be assessed using the Time-Line Follow-Back Interview (TLFB)[3, 4] self-reported as described in in the primary objective.

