9.3 Definition of Populations

Intent-to-treat and dose analyses will be used. Intent to treat analyses includes all participants enrolled in the study. The dose analyses will examine TAU vs. MABT participants who completed > 75% of the initial intervention. Exploratory dose analyses will assess the impact of additional MABT sessions in the subpopulation of MABT-assigned participants who report using substances at the 6 month assessment.

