9.6 Data Analyses

Primary Analysis To test the primary hypotheses, generalized linear regression models for dependent data will be used to compare percent days abstinent from opioid use in the two study groups between baseline to 6 months for the R33 study aims, and baseline to 12 months for the R01 study aims. Sensitivity analyses will also explore modeling opioid use as percent days abstinent during the assessment periods using Generalized Estimating Equations (GEE) [106] with a logit link and an exchangeable correlation structure. We will fit difference within group correlations structures (unstructured, independent, exchangeable, autoregressive) seeking the correlation structure that combines the fewest parameters with the best measure of fit using Akaike information criterion (AIC) and Bayesian information criterion (BIC). The logarithm of the total number of days in the assessment period will be included as an offset variable to account for the time at risk of relapse. The same analysis will be done to examine percent days abstinent on other illicit drugs and alcohol.

Secondary Analyses Analyses of secondary outcomes (mental and physical health outcomes and opioid craving) will utilize GEE as described above. Longitudinal analyses will examine treatment by time interactions on each of the outcomes. Analyses of retention in medication-assisted treatment will be done using a test of proportions retained in MAT as well as the log-rank test to compare survival curves. A sensitivity analysis will use Cox regression to adjust for pre-treatment covariates. Last, we plan to include exploratory analyses to also examine treatment by gender interactions.

Exploratory Analysis Linear regression model using GEE will be used to explore the effect of additional MABT dose on days abstinent from opioid use and related health outcomes at 12 months among the MABT 6 month non-responders compared to control non-responders. Characteristics of responders will be compared to those of non-responders using t-tests, chi-square, or Fisher's exact tests.

In addition, we will explore the relationship with dose, within the MABT group. Dose response functions will be estimated thorough a regression approach treating the number of sessions as the continuous treatment variable. Such models are appropriate when the treatment intensity is endogenous (that is, selection into treatment depends on both observable and unobservable factors).

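### The dose set's attendance cut contradicts its own session count, and the objective 3 hypothesis is worded for recipients while the analysis is as offered; the inputs to the exploratory power also need stating

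*Combined protocol and SAP*

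**What the plan says.** **Attendance cut.** Section 9.3 states: "The dose analyses will examine TAU vs. MABT participants who completed > 75% of the initial intervention". Section 5.4 uses the same strict inequality but adds in brackets that it means 6 to 8 sessions, because that many are needed to receive every component. The initial course is eight sessions.

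**Objective 3.** The hypothesis in 1.2 concerns "those in MABT group who receive additional MABT sessions (between 6-9 months"). Section 9.1 repeats it: "Among participants in both groups who are using substances at 6 months, those in MABT group who receive additional MABT sessions". The objective line in 1.2, the paragraph after the hypothesis in 9.1, and the exploratory power text in 9.2 all speak of sessions being offered. Section 9.6 compares "days abstinent from opioid use and related health outcomes at 12 months among the MABT 6 month non-responders compared to control non-responders". Section 9.3 mentions only the impact of "additional MABT sessions in the subpopulation of MABT-assigned participants who report using substances at the 6 month assessment" and names no TAU group.

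**Power.** For the exploratory aim, 9.2 assumes a 15-point difference in the proportion of abstinent days and says that power "is .65 for a 40% non-responder rate (n = 53 per group"). For the primary aim, 330 participants less 20% loss "allows for .80 power to detect a minimum difference in proportion in days abstinent between MABT and TAU of .14", at two-tailed alpha .05. The prior study's 12-month rates are given as 88.6 (MABT) and 80.0 (TAU). Neither power statement names the control rate, SD or test used.

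**The concern.** Two analysis sets can be built in more than one way from the text, so the choice could be made after the data are seen.

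- *Dose set.* A participant with exactly six sessions is in under 5.4's count and out under the inequality in both sections.
- *Objective 3.* If the MABT side is limited to those who took up the added sessions while the TAU side keeps all its non-responders, self-selection enters on one side only. Even as offered, the groups are defined by 6-month use, which is measured after randomisation and after the initial sessions, so randomisation does not protect the comparison.
- *Power.* Section 9.2 offers this aim as a basis for sizing later research. A reader who wants to use the figure needs to know what abstinence rate it assumes for non-responders.

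**Working it through.** **1. Attendance cut.** 6/8 = 0.75, which is not greater than 0.75; 7/8 = 0.875. The strict rule therefore means 7-8 sessions, while 5.4's count means 6-8. The share attending exactly six is not given. For each assumed 5%, 165 × 0.05 = 8.25, so about 8 people change status.

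**2. Objective 3 sets side by side.**

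| Place | MABT side | TAU side |
|---|---|---|
| 1.2 and 9.1, hypothesis | 6-month users who receive sessions | 6-month users |
| 1.2, objective line; 9.2 | 6-month users, offered sessions | 6-month users |
| 9.6 | all 6-month non-responders | control non-responders |
| 9.3 | MABT-assigned 6-month users | not named |

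With uptake u and a prognosis gap g between takers and decliners, taking recipients only shifts the MABT mean by (1 − u) × g. At an assumed u = 0.60 and g = 10 points this is 0.40 × 10 = 4 points, sign unknown.

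The as-offered set has a price. A 15-point effect in takers at 60% uptake becomes 15 × 0.60 = 9 points. With 53 per group and an assumed SD of 32.6 points (the SD at which 15 points has power .65), 9 / (32.6 × √(2/53)) = 1.42, and two-sided t-test power is 0.29.

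**3. Power figures.** Pooled two-proportion formula, two-sided .05, with p̄ the mean of the two rates:

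power = Φ{[d − 1.96 √(2p̄(1−p̄)/n)] / √[(p₁(1−p₁) + p₂(1−p₂))/n]}

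- *Exploratory, plan's figure.* n = 132 × 0.40 = 52.8, rounded to 53; 0.80 v 0.95. (0.15 − 1.96 × 0.0642)/0.0626 = 0.385, giving power **0.650**. The stated .65 reproduces using the prior TAU rate.
- *Primary at the same rate.* n = 330 × 0.80 / 2 = 132; 0.80 v 0.94. (0.14 − 1.96 × 0.0414)/0.0405 = 1.45, giving power **0.927**, not .80.
- *Primary from the printed MABT rate.* 0.886 − 0.14 = 0.746; 0.746 v 0.886 with continuity correction 1/n = 0.0076. (0.14 − 0.0076 − 1.96 × 0.0477)/0.0469 = 0.83, giving power **0.797**. This is close to the stated .80.
- *One method for both figures.* The control rates that return the stated powers differ: 0.719 (primary) and 0.800 (exploratory) pooled; 0.748 and 0.833 continuity-corrected.

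Exploratory power for 15 points at 53 per group, pooled:

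| TAU rate (assumed) | 0.84 | 0.80 | 0.72 | 0.60 |
|---|---|---|---|---|
| Power | 0.80 | 0.65 | 0.48 | 0.38 |

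**The case against.** *On the sets.* Section 5.4 explains why six sessions count, so the inequality is probably a slip for 'at least'. That supports a simple repair, but 9.3, the section an analyst would follow, has no session count. Most passages on objective 3 already describe the offered comparison. The sentence in 9.3 can also be read as the separate within-MABT dose analysis in 9.6. On that reading 9.3 does not contradict 9.6, but it still leaves the objective 3 comparator undefined.

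*On power.* Section 9.2 already calls the aim exploratory and underpowered, and .65 can be recovered from numbers printed there. Three stronger readings are tempting, and the documents support none of them.

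- *That the primary .14 is wrong and should be about .12.* This holds only if 0.80 was the control rate. The printed MABT rate less .14, with continuity correction, gives .797 at 132 per arm. Section 9.2 does not state that route either, but it prevents a finding of error.
- *That .14 was worked out for a smaller sample.* At 80% power, 0.4 SD needs only 100 per arm, and .14 from a TAU rate of 0.80 needs 90 (104 corrected). But 9.2 also claims 80% power for retention of 60% v 77%. That needs about 116 per arm: power is 0.69 to 0.76 at 90 to 104, and 0.85 at 132. The 0.4 SD statement is simply conservative.
- *That both calculations must share one input.* One concerns the full sample and the other a selected subgroup, so different inputs are not in themselves an error.

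Nor can the as-offered set be defended on power. Comparing it with recipients only at a fixed 15 points ignores the dilution shown above.

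**Conclusion.** The attendance cut is wrong as written, and the objective 3 hypothesis conflicts with the planned comparison. Both should be corrected. The effect is minor to moderate, because the dose and objective 3 analyses are secondary or exploratory and the primary analysis is untouched. The 8 people per 5%, the 4-point bias and the 0.29 power rest on assumed shares, uptake, prognosis gap and SD, since the documents give none of these.

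The power matter is a note on missing detail. The .65 appears to apply the prior study's whole-sample TAU rate to people chosen for continued use. The true rate could lie on either side, because selection is on any substance use apart from marijuana, with alcohol counted as heavy-drinking days (6.2.4), while the outcome is opioid-abstinent days. The range of 0.80 to 0.38 treats abstinent days as one binary proportion per person, as the match to .65 suggests. The documents do not show that .14 is wrong.

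**What to change.** 1. **Sections 5.4 and 9.3:** use one attendance cut in both. At least 75%, that is 6 to 8 sessions, agrees with the reason 5.4 gives. Report the attender-versus-TAU result as subject to selection bias.
2. **Sections 1.2 and 9.1:** change *receive* to *are offered* in the objective 3 hypothesis. **Section 9.3:** name the TAU 6-month non-responders as the comparator. **Section 9.6:** adjust for baseline days of opioid use, already collected by the baseline TLFB, and describe the result as a non-randomised comparison because 6-month use is measured after randomisation.
3. **Section 9.2:** for each power figure, state the control rate or SD, the test and the sidedness. Replace the single .65 with the range 0.80, 0.65, 0.48 and 0.38 at TAU rates of 0.84, 0.80, 0.72 and 0.60, and say which rate is expected in non-responders and why. The .14 need not be changed, and the two calculations need not share an input.

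The cost is wording in five sections and one covariate already in the data. The downsides are a less tidy power statement and, if uptake is low, a diluted as-offered effect.

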9.3 Definition of Populations

Intent-to-treat and dose analyses will be used. Intent to treat analyses includes all participants enrolled in the study. The dose analyses will examine TAU vs. MABT participants who completed > 75% of the initial intervention. Exploratory dose analyses will assess the impact of additional MABT sessions in the subpopulation of MABT-assigned participants who report using substances at the 6 month assessment.

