MABT Reduces Psychological Symptoms and Improves Emotional Well-being, Mindfulness, and Interoceptive Skills: MABT SUD treatment research (R21 study) showed promising results with significant between-group differences with moderate to large effects on mental health outcomes between MABT+TAU compared to TAU at 9 months. These included depression symptoms, eating disorder symptoms, perceived stress, dissociation, and physical symptom frequency.[85] The R01 pre-post findings (N = 187) showed significant improvements for MABT compared to TAU in craving, depression among those that received the full intervention dose, improved emotion regulation (self-report and psychophysiology), interoceptive awareness, and mindfulness skills among the MABT completers.[89]. Longitudinal outcomes showed maintained improvements for MABT vs. TAU on craving, psychophysiology (well-being/regulation), interoceptive awareness and mindfulness skills.[90] The proposed study examines many of the same mental health and process variables as in the above studies.

Patients on MAT frequently suffer from chronic pain, which is a risk factor for opiate craving

and potential relapse. We conducted a cross-sectional study (K23DA027367) of 106 adults who were maintained on buprenorphine or methadone.[91] The primary outcome was cold pain tolerance assessed by cold-pressor test. Chronic pain was highly prevalent (67%), and current pain was even moreso (83%). These results reinforced that pain and hyperalgesia are common problems in this population of persons who were maintained on MAT for treatment of OUD. In a subsequent study performing secondary analysis on data from the same sample, we examined relationships between pain and opioid craving and opioid use as measured by urine drug testing (UDT).[92] We found that 51% reported craving opioids in the past week, and 16% had a positive UDT for opiates. We concluded that chronic pain with associated opioid craving potentially places this population at risk for relapse. Results from these two studies underscore that there is an unmet need for interventions to address pain among persons on MAT in order to prevent relapse and improve addiction treatment outcomes.

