5.2 Handling of Study Interventions

Mindful Awareness in Body-oriented Therapy (MABT): The MABT intervention has a well-developed protocol and training manual for research. Used in multiple clinical trials,[83, 85, 86, 93-95] the protocol has an incremental approach for teaching interoceptive awareness skills and developing weekly individualized homework based on session content to promote integration of practice into daily life. Individuals in the MABT treatment group will receive 8 weekly 1.25 hour one-on-one sessions of MABT. Research therapists will be hired and trained to provide the MABT intervention. MABT has three distinct stages (see Table 2). Stage 1 (sessions 1-2), develops body literacy, the ability to identify and articulate sensory awareness. Body literacy training is done in the context of massage therapy to facilitate sensory awareness related to attention to the quality of soft tissue (e.g., muscular tension). Stage 2 (sessions 3-4) focus on interoceptive awareness training to develop the ability to access inner body awareness and begin to make links between physical and emotional sensations. Stage 3 (sessions 5-8) focuses on the development and practice of mindful body awareness involving sustained interoceptive attention which facilitates positive shifts in sensory experience as well as insights that motivate behavior change. Each session begins with a semi-structured check-in to build trust and familiarity between therapist and participant, and ends with session review to facilitate cognitive integration of the session

material and to collaboratively develop the homework for the interim week. The interoceptive training components (stages 1-3) are designed with an incremental approach to facilitate learning, particularly important for individuals with SUD who often have difficulties attending to sensory (physical and emotional) awareness. Individualized homework is based on session content and crafted to promote integration of practice into daily life.

The additional six MABT sessions that will be offered to eligible participants at 6 months will be delivered as explained above and will include all stages of the intervention as outlined in Table 2 but will be individualized to address the intervention components needing the most review (if the participant did not complete MABT initially) or will follow the intervention protocol for delivery of the first 6 of 8 sessions if the received no prior MABT sessions when initially assigned.

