5.4 Adherence Assessment

To assess adherence to the study intervention we will record number of sessions attended. In addition to an intent-to-treat analysis, we will also examine MABT dose. Specifically, we will examine outcomes for participants who attended > 75% of the initial intervention sessions (i.e. 6-8 sessions) between baseline and 3 months, as this is the number of sessions needed in order to receive all intervention components, compared to TAU. We will also record the number of additional sessions received by eligible participants between 6 and 9 months.

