8. INTERVENTION DISCONTINUATION

MABT sessions will be discontinued for any of the following reasons, but participant will not be withdrawn from study:

1. Participants are inebriated or high from alcohol or drugs such that they are not able to engage in the intervention on more than one scheduled session.
2. If, in consultation with the participant's healthcare providers, there is concern for his/her safety and well-being (e.g., escalation of symptoms).

The participant could be withdrawn from study if, in consultation with the participant's health care providers, there is sufficient concern for his/her safety and well-being that the

participant may be withdrawn and re-directed to more appropriate care. This is described to the participant in the consent process.

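### The completer cut-off contradicts itself (more than 75% of eight sessions is 7-8, yet 5.4 says 6-8), and 9.6 wrongly calls a regression on session count appropriate under unobserved selection

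*Combined protocol and SAP*

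**What the plan says.** Four analyses that depend on sessions received or offered sit beside the intention-to-treat analysis.

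- **Attender comparison.** Section 5.4 defines the attenders as "participants who attended > 75% of the initial intervention sessions (i.e. 6-8 sessions"), counting attendance up to the 3-month assessment, and compares them with TAU. The reason it gives is "as this is the number of sessions needed in order to receive all intervention components". Section 9.3 repeats the percentage without a session count: "The dose analyses will examine TAU vs. MABT participants who completed > 75% of the initial intervention".
- **Session regression.** Section 9.6 plans a regression within the MABT arm with number of sessions as a continuous treatment variable, and says "Such models are appropriate when the treatment intensity is endogenous", explaining this as selection on both observable and unobservable factors.
- **Added sessions.** Section 5.4 says "We will also record the number of additional sessions received by eligible participants between 6 and 9 months".
- **Objective 3.** The hypothesis in sections 1.2 and 9.1 concerns 6-month users in the MABT arm who *receive* added sessions, compared with 6-month users in TAU. Section 9.3 speaks of the *impact* of those sessions and section 9.6 of their *effect*.

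Section 8 bears on attendance. One of its grounds for stopping MABT sessions is "Participants are inebriated or high from alcohol or drugs such that they are not able to engage in the intervention". The stop applies once this has happened at two or more visits, and follow-up continues.

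**The concern.** **Cut-off.** The percentage and the session range describe different sets of people. An analyst working from 9.3 alone would build a smaller set than one working from 5.4, and while both stand the choice could be made after the data are seen.

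**Session regression.** Ordinary regression does not remove selection on unmeasured factors. The 9.6 sentence says the reverse of what a reader needs to know, and could lead a dose gradient to be read as causal.

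**Attender comparison.** It sets a self-selected part of one arm against the whole of the other. Because sessions stop after repeated intoxication, attendance can partly reflect substance use, which is the outcome domain.

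**Objective 3.** Six-month users are defined after randomisation in each arm. A difference between them at 12 months mixes the added sessions with whatever the first course did, including whom it left in the group.

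**Working it through.** **1. Cut-off.** Inputs: eight initial sessions (5.1); more than 75% (5.4, 9.3); six to eight sessions (5.4).

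6/8 = 75.0%, 7/8 = 87.5%, 8/8 = 100%. *More than 75%* gives 7-8 sessions. The plan's 6-8 is reproduced only by *at least 75%*.

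The sets differ by those with exactly six sessions. With assumed independent per-session attendance q and 165 people in the arm, that number is 165 × 28 × q^6 × (1-q)^2:

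| q (assumed) | exactly six | six or more | seven or more |
|---|---|---|---|
| 0.70 | 49 | 91 | 42 |
| 0.75 | 51 | 112 | 61 |
| 0.80 | 48 | 131 | 83 |
| 0.90 | 25 | 159 | 134 |

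Attendance probably clusters within person. A beta-binomial with within-person correlation 0.3 gives 23, 20 and 12 people at exactly six for q = 0.7, 0.8 and 0.9.

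**2. Session regression.** Set side by side, section 9.6 claims validity under unobserved selection but names no instrument, control function, selection equation or covariates for this model. Randomised arm cannot be the instrument, because it is constant within one arm.

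An illustration with assumed inputs: 132 per arm, no true effect, one unmeasured factor driving both attendance and outcome, nominal 5% two-sided test. With a factor-outcome correlation of 0, 0.2 or 0.4, the session slope is significant in 5%, 45% or 97% of simulated trials. The intention-to-treat test stays at 5%.

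Section 9.6 also does not say which sessions count. A person abstinent at 6 months can have at most 8. A 6-month user can have 8 + 6 = 14. A total would therefore mix early exposure with sessions triggered by later use.

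**3. Attender comparison.** Suppose there is no true effect, a share p of the MABT arm are attenders, and attenders differ from non-attenders by a gap in percent days abstinent. The attender-minus-TAU bias is then (1-p) × gap.

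The prior-study difference in section 9.2 is 88.6 - 80.0 = 8.6 points, and half of that is 4.3. The gap needed for selection alone to produce 4.3 points is:

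- p = 0.6: 4.3/0.4 = 10.8 points
- p = 0.7: 4.3/0.3 = 14.3 points
- p = 0.8: 4.3/0.2 = 21.5 points

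So the bias matters mainly if completion is low. The values of p are assumed, and the formula concerns levels. In a model of change from baseline, selection would have to act on change.

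**4. Objective 3.** No arithmetic is needed. Randomisation balances the arms, not the subsets still using at 6 months. The hypothesis says *receive*, whereas sections 5.1 and 9.2 say *offered*. These define different groups whenever an offer is declined.

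**The case against.** The strongest reply on the cut-off is that 5.4 gives the session count and a reason, and 9.3 merely repeats the percentage as shorthand. On that view it is a one-symbol correction. A symbol lost in reading the PDF cannot be excluded either, although the mark appears in both sections and 9.1 prints the at-least form for heavy-drinking days. This stands as to severity, but the text still needs reconciling.

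A reader might infer that the stage structure proves six sessions to be right. It does not: "Stage 3 (sessions 5-8) focuses on the development and practice of mindful body awareness", so five sessions already reach every stage. Six to eight is preferred only because it is the sole session count the plan states.

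On the attender comparison, 5.4 places it in addition to intention-to-treat. A reader might point to section 2.2, which reports improvement in "depression among those that received the full intervention dose", as a sign that such results get presented without a label. That passage does label them as results in full-dose recipients and completers, so it does not support the inference.

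On 9.6, the sentence shows awareness of selection, the analysis is exploratory, and *such models* may mean an unnamed endogenous-dose method. That is fair, and naming the method would be an acceptable repair. Sections 5.4 and 9.3 do separate initial from added sessions, so counting both is a gap in 9.6, not a stated intention.

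On Objective 3, section 9.2 already calls it exploratory and underpowered, and several sections name the TAU comparator. A reader might infer that, with useless added sessions, the comparison could as easily go against MABT as for it. The plan's own assumption does not support that. Section 9.2 expects similar effects to 6 and to 12 months, and section 2.2 reports prior differences at both. If the first-course effect lasts fully, an illustrative logit-normal model of daily abstinence (80.0% TAU, 88.6% MABT, user = any use in 90 days, assumed person SD 4 to 10) gives gaps of about +7 to +8 points with no added-session effect. Those gaps are all positive. What remains is that the comparison cannot isolate the added sessions.

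**Conclusion.** Two statements are wrong as written: the cut-off in 5.4 and 9.3, and the sentence in 9.6 on unobserved selection. The first is exact arithmetic and needs no assumption. Its effect on the size of the completer set cannot be known from the documents; 25-51 people (independent attendance) or 12-23 (clustered) are illustrations. The second rests on the absence of any named identifying method.

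The missing caveat on the attender comparison and the wording of Objective 3 are cheap improvements, not errors that change a result. The size of any attender bias depends on completion and on the attender gap, neither of which the plan gives.

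Overall severity is minor. A reader might take these points to threaten the trial's main conclusion. They do not: the intention-to-treat analysis, the sample size and the primary result do not depend on any of these analyses.

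**What to change.** 1. **Sections 5.4 and 9.3:** use one analysis-set rule in both, *at least 75% (6-8 sessions)*.
2. **Section 9.6, session regression:** delete the sentence on endogenous dose and report an association adjusted for baseline use and the minimisation factors (site, sex, chronic pain), using initial sessions only. Alternatively, name a method that handles endogenous dose and state its assumptions.
3. **Sections 5.4 and 9.3, attender comparison:** label it non-randomised and supportive. Account for baseline use (as a covariate, or through the baseline time point if the longitudinal model is used) and for the minimisation factors. State that unmeasured selection remains.
4. **Objective 3:** replace *impact* (9.3) and *effect* (9.6) with descriptive wording that does not credit the added sessions alone, and change *receive* to *are offered* in the hypothesis (1.2, 9.1).

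Cost: text edits in 1.2, 5.4, 9.1, 9.3 and 9.6, and a little more analysis work for the adjusted models. The covariates are already collected at baseline, so no new data are needed. The downside is that the attender, session and Objective 3 results will support weaker conclusions.
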